8.2 Exclusion Criteria

8.21 Patients who rated their fatigue level at 4 or less over the past 24 hours based on the fatigue at its worst item of the BFI.

8.22 Patients with clinical evidence of active persistent cancer or progressive disease after completing planned cancer therapy, or with active recurrent cancer.

8.23 Patients with potential medical or other underlying causes of fatigue, as determined by the treating physician or PI.

8.24 Patients with Hb <10.5 g/dL within previous 2 weeks.

8.25 Patients with untreated or uncontrolled hypothyroidism, or TSH $>$ ULN or free T4 $<$ lower level of normal within previous 2 weeks.

8.26 Patients with underlying cardiac or pulmonary disease resulting in dyspnea, hypoxia, or hypercapnea.

8.27 Patients with a Karnofsky performance status <70

8.28 Patients less than 18 years old

8.29 Patients who are enrolled and receiving active treatment in other symptom intervention trials or who are in the treatment phase of another clinical trial

8.210 Patients with pre-existing psychosis or bipolar disorder

8.211 Patients with pre-existing renal impairment, as evidenced by serum creatinine $>$ ULN on the most recent blood work, done at least within the previous 2 weeks.

8.212 Patients with pre-existing cirrhosis or hepatic impairment or with abnormal liver function test as evidenced by total bilirubin $>1.5 \times$ ULN or 2 times the upper limit of normal of alkaline phosphatase (ALP), alanine aminotransferase (ALT) or aspartate aminotransferase (AST) on the most recent blood work, done at least within the previous 2 weeks.

8.213 Patients with pre-existing Tourette's syndrome

8.214 Patients who have used monoamine oxidase (MAO inhibitors) within the past 14 days

8.215 Patients undergoing abrupt discontinuation of ethanol or sedatives (including benzodiazepines)

8.216 Patients currently taking, or having taken within the previous 1 month, armodafinil, modafinil, amphetamine, or methylphenidate

8.217 Patients on anticoagulants (i.e. warfarin, coumadin, or heparin) or clopidogrel

8.218 Patients with a history of clinically significant cutaneous drug reaction, or a history of clinically significant hypersensitivity reaction, including multiple allergies or drug reactions

8.219 Patients with a history of angina or cardiac ischemia, a recent history of myocardial infarction (within the past 1 year) or left ventricular hypertrophy, or patients with mitral valve prolapse

8.220 Patients with uncontrolled hypertension or tachycardia, as determined by treating physician

8.221 Patients who are pregnant, breastfeeding, or planning to become pregnant during the study period and for 1 month after stopping the study drug.

8.222 Female patients who are currently on birth control pills as primary means of contraception, but are not willing to seek an additional effective method of contraception (such as barrier method) during the study period and for 1 month after stopping the study drug.

8.223 Patients with a history of CNS stimulant abuse, such as methylphenidate, dextroamphetamine, or modafinil.

8.224 Patients with major depressive disorder or severe depression (a score of 13 or greater on the BDI Fast Screen (BDI-FS) will be excluded. If this is the case, we will notify their treating physician for appropriate management or referral.

8.225 Patients with current or a history of suicidal ideation.

8.226 Patients currently taking midazolam, cyclosporine, ethinyl estradiol, or triazolam

8.227 Patients currently taking carbamazepine, phenobarbital, rifampin, aminoglutethimide, naftilin, nevirapine, phenytoin, azole antifungals, clarithromycin, diclofenac, doxycycline, erythromycin, imatinib, isoniazid, nefazodone, nicardipine, propofol, protease inhibitors, quinidine, telithromycin, or verapamil

8.228 Patients currently taking omeprazole, diazepam, propanolol, chlomipramine (or other tricyclic antidepressants), citalopram, methsuximide, or sertraline.

9.0 Patient Enrollment and Registration

Patient Enrollment

Patients will be screened for eligibility and recruited for enrollment in the outpatient Head and Neck Cancer Clinic in the Department of Radiation Oncology at MD Anderson, 6 or more weeks after completing planned cancer therapy (this time line will generally coincide with the first follow up appointment for most patients with HNC treated with radiation therapy). By this time, most patients should have had significant improvement in their radiation therapy-related mucositis, dermatitis, and pain. Recruitment brochures will be available to give to the patients in the clinic (Appendices ZZ and ZZZ).

Patients with major depressive disorder or severe depression (a score of 13 or greater on the BDI Fast Screen (BDI-FS) will be excluded. If this is the case, we will notify their treating physician for appropriate management or referral. The first disease/treatment response assessment is made around this time period as well.

Women of child-bearing potential who want to participate will be told that we will perform a mandatory pregnancy screening test through a urine sample at baseline. Study staff will provide the pregnancy kits to these women and make sure the results are known and recorded in the follow-up notes in Clinic Station before study drug prescription are filled by the Investigational Pharmacy. If the pregnancy test is positive the patient will be excluded from the study.

Research staff will maintain a log of all patients screened, and the reasons that patients do not enter the study will be documented.

Eligible patients who agree to enroll in the study will provide written informed consent/authorization.

At enrollment, patients will be informed that they will receive a \$40 stipend for participating in the pilot study. The stipend will be distributed in \$20 increments twice during the study, at enrollment and at study completion.

Enrolled patients will be registered into the Clinical Oncology Research System (CORe), the MD Anderson institutional patient data management system.

Patient Randomization and Assignment to Treatment Arm

The study will accrue 40 patients who will be randomized into 2 arms (armodafinil and placebo), with 20 patients each (see Section 5.0 Study Design). Prior to accruing the first patient, a randomization list will be generated by our biostatistician collaborator from the Department of Biostatistics for all 40 patients, stating to which group a patient was randomized. This list containing the accrual number and treatment group information will be given to Investigational Pharmacy. A sealed backup list will be kept by the assigned data analyst in the Department of Symptom Research. This list will be opened only if unblinding is needed.

Once a patient is enrolled, study staff will inform the Investigational Pharmacy of the patient's accrual number and patient ID. Once a patient is randomized to a treatment arm, the Investigational Pharmacy will retrieve the randomized treatment arm information from the generated randomization list and will relay that information to the dispensing Pharmacy. The patient may visit the most convenient outpatient pharmacy to pick up the study medication assigned.

10.0 Assessment Schedule

Please see Appendix X for an expanded study assessment/evaluation schedule.

Data Confidentiality Plan

All patient-reported outcome, laboratory, and clinical data gathered in this protocol will be stored in a password-protected database. All patient information will be handled using anonymous identifiers. Linkage to patient identity is only possible after accessing a password-protected database. Access to the database is only available to individuals directly involved in the study.

When all analysis has been completed and all study results have been reported, the electronic and paper files will be stored in a password-protected MD Anderson secure server. This stored data may be made available to MD Anderson research and

clinical faculty for research purposes, with appropriate validation and access controls, so it can facilitate research cross-fertilization and speed insight discovery. Patient data also will be stored and accessible in the MD Anderson Translational Research Accelerator database (TRA; PI: [name]).

11.0 Adverse Event Reporting

11.1 Adverse Events (AE) (Appendix I)

Telephone monitoring will be conducted by study staff weekly over the entire study period. Patients can contact study staff at any time during study period through the study hotline with questions or concerns regarding potential side effects of study medication. In addition, patients can be seen by either the treating physician or the PI as needed.

Treatment-related toxicities (NCI Common Terminology Criteria for Adverse Events, version 4) will be monitored by both clinic and research staff weekly either by phone or during any regular clinical appointments as described above. Other clinical variables will be collected as described in the Assessment Schedule. (Appendix X - AE Form).

Expected (due to previous cancer treatment or symptom treatment) or unrelated grade 1 or 2 toxicities will not be reported. AEs that are grade 3 and above that are definite, probable, or possible and related will be reported. AEs will be tabulated and reported as a summary on the continuing review report. All grade 3 and 4 toxicities will be evaluated by the PI and treating physician to determine if the toxicities were due to study medication.

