4.2 Armodafinil Common Adverse Reactions

Most commonly reported adverse reactions: headache, nausea, dizziness, and insomnia

- 4.21 Occurring in greater than >10% of study subjects across randomized studies with armodafinil:

Central nervous system: Headache (14% to 23%)

- 4.22 Occurring in 1% to 10% of study subjects across randomized studies with armodafinil:

Cardiovascular: Palpitation (2%), increased heart rate (1%)

Central nervous system: Dizziness (5%), insomnia (4% to 6%; dose related), anxiety (4%), depression (1% to 3%; dose related), fatigue (2%), agitation (1%), attention disturbance (1%), depressed mood (1%), migraine (1%), nervousness (1%), pain (1%), pyrexia (1%), tremor (1%)

Dermatologic: Rash (1% to 4%; dose related), contact dermatitis (1%), hyperhidrosis (1%)

Gastrointestinal: Nausea (6% to 9%; dose related), xerostomia (2% to 7%; dose related), diarrhea (4%), abdominal pain (2%), dyspepsia (2%), anorexia (1%), appetite decreased (1%), constipation (1%), loose stools (1%), vomiting (1%)

Genitourinary: Polyuria (1%)

Hepatic: GGT increased (1%)

Neuromuscular & skeletal: Paresthesia (1%)

Respiratory: Dyspnea (1%)

Miscellaneous: Flu-like syndrome (1%), thirst (1%)

- 4.23 Postmarketing and/or case reports: Anaphylactoid reaction, angioedema, hypersensitivity, liver enzymes increased, pancytopenia, systolic blood pressure increased (see section on Serious adverse events for symptom drug below)

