A list of adverse events (AEs) known to be associated with primary treatment is listed in section 4.0 of the protocol. Study staff will monitor for AEs via telephone contact with the subjects using the Phone Contact Form according to the Assessment Schedule. In addition, study participants will be able to contact study personnel via a telephone hotline, and study participants can be seen by study personnel at MD Anderson if there are any concerns or questions regarding potential side effects. If seen in person by study personnel, clinical monitoring form will be completed. Also, if study subjects are coming to MD Anderson for

routine clinical follow up (visits unrelated to this study), they will be seen by study staff as frequently as weekly during the study period, and the clinical monitoring form will be completed every time.

Patients will be advised to discontinue drug at first sign of body rash during this study and to immediately notify study personnel, who will in turn notify the PI for appropriate medical management.

All grade 3 and 4 toxicities reported by patients in this trial will be evaluated by the principal investigator in consultation with the treating physician, or by another attending physician if the PI is not available, to determine whether the toxicities were possibly caused by the study medication (rather than being effects from previous cancer therapy). The investigators will discriminate between expected dermatitis related to radiation therapy or chemotherapy versus armodafinil hypersensitivity. If 1 or more armodafinil-related grade 3 or 4 toxicities is observed in the patients assigned to armodafinil, the study will be terminated.

The interaction screening will be the responsibility of the research staff. Study exclusion criteria of known drug interactions and drugs that would require additional monitoring if given in conjunction with armodafinil will also be in place for patient safety. The research staff will review any current or new patient medications prior to initiating treatment, and will document all medications patients have used or will use during the trial. During the trial, the research staff will capture any potential drug interactions that could cause an AE on the Adverse Event forms. Medication sheets will be provided to both patients and treating physicians to inform them of the possibility that the patients may be receiving armodafinil (see Appendix EEE and EE).

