7.5 Work Productivity and Activity Impairment Questionnaire (WPAI) (Appendix H)

7.6 Head and Neck Treatment Summary Form (Appendix O)

7.7 Patient Contact Form (Appendix P)

7.8 Demographic Form The Demographic Form includes patient birth date, gender, marital status, race, ethnicity, education, and employment status (Appendix Q). The Demographic Form will be completed at baseline.

7.9 Charlson Comorbidity Index The Charlson Comorbidity Index yields a comorbidity score, to control for serious concurrent chronic disease conditions (Charlson et al., 1994) (Appendix R).

7.10 On-Study Form The On-Study Form contains data about disease, previous treatment, whether a patient is on concurrent protocols (Appendix S). This form will be completed at baseline.

7.11 Clinical Monitoring Form The Clinical Monitoring Form contains clinical data, including Body Mass Index (BMI), blood pressure, pulse rate, performance status, symptom treatment, and CTC toxicity scores (Appendix T).

7.12 Medication Form The Medication Form contains data about types of medications patients have been prescribed. Medication types include pain medications, antiemetics, and psychotropics among others. There is also a general section for other types of medications patients may be taking. (See Appendix U).

7.13 Patient Disposition Form Patient's final disposition will be collected on the Patient Disposition Form. Patients who are satisfied with the study medication and express interest in continuing will be able to discuss continuing armodafinil as part of physician-patient decision based on a risk-benefit scenario, with further clinical monitoring to continue under the care of the patient's treating physician. Subjects with persistent moderate to severe levels of fatigue will be offered further evaluation and referral to the MD Anderson Fatigue Clinic (Appendix V).

7.14 Study Medication Accountability Form This form contains study medication data, including the number of tablets dispensed to the patient at the last visit to the outpatient pharmacy, how many tablets were returned from the last visit, and the number of days the tablets were taken (Appendix K).

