11.2 Serious Adverse Events (SAE) (Appendix J)

A serious adverse event is any adverse drug experience occurring at any dose that results in any of the following outcomes:

- Death.
- A life-threatening adverse drug experience – any adverse experience that places the patient, in the view of the initial reporter, at immediate risk of death from the adverse experience as it occurred. It does not include an adverse experience that, had it occurred in a more severe form, might have caused death.
- Inpatient hospitalization or prolongation of existing hospitalization.
- A persistent or significant disability/incapacity – a substantial disruption of a person's ability to conduct normal life functions.
- A congenital anomaly/birth defect.

Important medical events that may not result in death, be life-threatening, or require hospitalization may be considered a serious adverse drug experience when, based upon appropriate medical judgment, they may jeopardize the patient or subject and may require medical or surgical intervention to prevent one of the outcomes listed in this definition. Examples of such medical events include allergic bronchospasm requiring intensive treatment in an emergency room or at home, blood dyscrasias or convulsions that do not result in inpatient hospitalization, or the development of drug dependency or drug abuse (21 CFR 312.32).

Important medical events as defined above, may also be considered serious adverse events. Any important medical event can and should be reported as an SAE if deemed appropriate by the PI or the IND Sponsor, The University of Texas MD Anderson Cancer Center Institutional Review Board system (UTMDACC IRB) .

All events occurring during the conduct of a protocol and meeting the definition of a SAE must be reported to the IRB in accordance with the timeframes and procedures outlined in "The University of Texas MD Anderson Cancer Center Institutional Review Board Policy on Reporting Serious Adverse Events". Unless stated otherwise in the protocol, all SAEs, expected or unexpected, must be reported to UTMDACC IRB, regardless of attribution (within **5 working days** of knowledge of the event).

All life-threatening or fatal events, expected or unexpected, and regardless of attribution to the study drug, require a written report to be submitted within **24 hours** (next working day) of knowledge of the event to the Safety Project Manager in UTMDACC IRB .

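### Section 11.1 leaves expected low-grade toxicities unreported and Section 13 plans no adverse-event summary by arm, so armodafinil's common side effects have no planned comparison with placebo

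*Combined protocol and SAP*

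**What the plan says.** Section 11.1 of the combined protocol and SAP sets two filters. For low grades: "Expected (due to previous cancer treatment or symptom treatment) or unrelated grade 1 or 2 toxicities will not be reported". For higher grades: "AEs that are grade 3 and above that are definite, probable, or possible and related will be reported". It then says what becomes of the events: "AEs will be tabulated and reported as a summary on the continuing review report". No breakdown by arm is mentioned.

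Section 11.2 is wider for serious events: "all SAEs, expected or unexpected, must be reported to UTMDACC IRB, regardless of attribution".

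On ascertainment, Section 11.1 says that treatment-related toxicities, graded by CTCAE version 4, "will be monitored by both clinic and research staff weekly either by phone or during any regular clinical appointments as described above". Section 5.0 provides a Phone Contact Form for adverse-event monitoring by telephone and refers to Adverse Event forms. The Clinical Monitoring Form (Section 7.11) holds "performance status, symptom treatment, and CTC toxicity scores", but Section 5.0 ties it to in-person contact: "If seen in person by study personnel, clinical monitoring form will be completed".

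Section 4.2 names the reactions to look for: "Most commonly reported adverse reactions: headache, nausea, dizziness, and insomnia". Section 13 covers sample size, the fatigue AUC, secondary patient-reported outcomes, satisfaction with study drug by arm, exploratory survival models and non-compliance. It has no adverse-event summary.

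**The concern.** Section 5.0 names armodafinil as the symptom intervention agent, so toxicity expected from symptom treatment is toxicity expected from the study drug. The 11.1 rule therefore leaves out the low-grade effects already known for the drug. It also filters on attribution. These patients carry residual effects of radiation and chemotherapy, and Section 5.0 itself foresees having to tell radiation or chemotherapy dermatitis from armodafinil hypersensitivity. A blinded randomised placebo arm makes that separation at group level without case-by-case judgement, but only if events are tabulated by arm before they are filtered.

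At stake is tolerability information. Section 4.0 reports that the authors know of no published cancer study of armodafinil, Section 2.0 presents it as a low-toxicity therapy, and Sections 13.1 and 13.2 say that the results will help design a larger trial. That later trial would want side-effect frequencies by arm in this population, and the plan does not commit to producing them.

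**Working it through.** **Step 1. Sort events by the stated rules.**

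| Event | Reported? | Source |
|---|---|---|
| Serious, any cause | Yes | 11.2 |
| Non-serious, grade 3+, at least possibly related | Yes | 11.1 |
| Non-serious, grade 3+, unrelated | Not among those to be reported | 11.1 |
| Non-serious, grade 1-2, unexpected and related | Not excluded | 11.1 |
| Non-serious, grade 1-2, expected from prior cancer therapy or armodafinil | No | 11.1 |
| Non-serious, grade 1-2, unrelated | No | 11.1 |

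The Section 4.2 reactions, when mild or moderate, fall in the fifth row. Because staff are blinded in Part I, the filter should act alike in both arms. The comparison is therefore left out rather than tilted.

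**Step 2. Look for a by-arm account elsewhere.** The only tabulation is the continuing-review summary in 11.1. Section 13 compares drug satisfaction between arms but not adverse events.

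**Step 3. Expected numbers affected.** Inputs: 20 armodafinil patients (13.1) and the rates in 4.21 and 4.22. Expected count = 20 × rate.

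- Headache, 14% to 23%: 20 × 0.14 = 2.8; 20 × 0.23 = 4.6
- Nausea, 6% to 9%: 20 × 0.06 = 1.2; 20 × 0.09 = 1.8
- Dizziness, 5%: 20 × 0.05 = 1.0
- Insomnia, 4% to 6%: 20 × 0.04 = 0.8; 20 × 0.06 = 1.2

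The chance that at least one of 20 has headache is 1 − 0.86^20 = 95% at the low rate and 1 − 0.77^20 = 99.5% at the high rate. The protocol gives no split by grade. If all are non-serious and grade 1-2 (assumed), the number reported under 11.1 is zero.

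**Step 4. What an unfiltered table could show.** The documents give no placebo rate for headache, so 5% and 10% are assumed. Power of a two-sided 5% Fisher exact test with 20 per arm:

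| Armodafinil | Placebo (assumed) | Power |
|---|---|---|
| 23% | 5% | 24% |
| 23% | 10% | 11% |
| 14% | 5% | 6% |
| 14% | 10% | 2% |

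Against 0/20 on placebo, 4/20 gives p = 0.106 and 5/20 gives p = 0.047, so at least five cases are needed. For 23% against 10%, the 95% interval half-width is 1.96 × √(0.23×0.77/20 + 0.10×0.90/20) = 0.227, about 23 percentage points.

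**Step 5. The plan's own design figure.** Section 13.1 gives 70% power for 0.70 SD with 20 per arm, one-sided 5%. The noncentral t with 38 degrees of freedom and noncentrality 0.70 × √(20/2) = 2.21 gives 70.2%, so the figure reproduces. It concerns fatigue and has no bearing on this point.

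**The case against.** The strongest reply is that 11.1 governs reporting, not recording. It sits in the reporting section, ends in the continuing-review summary, and nowhere says that low-grade events go unrecorded. Toxicity is monitored weekly in both arms, and telephone contacts have their own form. This stands. A reader might infer that the trial cannot compare side effects between arms; the documents do not support that, because the data may well be collected. They do not settle it either. The weekly monitoring is worded around treatment-related toxicity, the form known to hold toxicity scores depends on in-person contact, and the adverse-event form and assessment schedule are in appendices not available for this review.

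A reader might also infer that only related grade 3+ events are reported. That is wrong: serious events are reported regardless of cause, and unexpected related low-grade events are not excluded. Nor does the Section 5.0 rule ending the study at the first armodafinil-related grade 3 or 4 toxicity in that arm mean that the safety data can hold only zero or one event. That rule concerns one class of event and does not limit the others.

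It is also fair to say that Section 1.0 has no safety objective, that no benefit-risk conclusion is planned, and that without placebo rates for these reactions one cannot say how far they would differ by arm. Finally, 20 per arm cannot test such differences. That limits what a table can prove, but the trial's stated purpose is estimation, and a descriptive table fits it.

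**Conclusion.** The point holds as a gap in the planned analysis. Under 11.1, expected low-grade drug effects are left out of reporting, and non-serious grade 3+ events are filtered by attribution. No section plans an adverse-event summary by arm. Its size is modest in patient numbers: about 2.8 to 4.6 expected headaches in the armodafinil arm and one or two patients for each of nausea, dizziness and insomnia. These are nonetheless the reactions the protocol calls most common.

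The conclusion assumes that symptom treatment in 11.1 means the study drug, that these reactions are non-serious and mostly grade 1-2, and that rates from other armodafinil studies carry over to this population. It does not claim that the data are lost, that reporting is confined to related severe events, or that a formal safety test is feasible. The change is worth making because it is cheap and the weekly contacts are already planned.

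**What to change.** Keep Section 11.1 as the rule for reporting to the IRB, and say so explicitly. Add a sentence that adverse events of every grade found at the planned weekly telephone or clinic contacts are recorded in both arms, with CTCAE grade, regardless of expectedness or attribution, and that telephone contacts capture the same items as clinic contacts.

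Add to Section 13 a descriptive table for Part I by randomised arm: patients with each event, by worst grade, with counts and percentages. Attribution may be shown as a further column but should not decide inclusion. Count every randomised patient who took study medication, including any later replaced under Section 13.2. Show open-label events separately, since patients from either arm may then be taking armodafinil. State that no hypothesis test is planned.

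The cost is entry of low-grade events at contacts that already take place (40 patients × 4 weeks = 160 in Part I) and one table. Sample size, visits and the primary analysis are unchanged.
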